3.3 RISK/BENEFIT ASSESSMENT

3.3.1 KNOWN POTENTIAL RISKS

Risk of Active Study Drug

Potential risks of active study drug (CO) include headache and tachycardia. In cases of overdose, patients can have nausea, vomiting, seizures, problems thinking, coma, cardiopulmonary arrest, and death. These adverse effects are seen at doses much higher than those proposed in this study. Subjects will be vigilantly monitored for side effects during drug administration and COHb and lactate levels will be carefully monitored as outlined in the study protocol. There may be other risks of inhaled CO in patients with ARDS that are currently unknown. Subjects will be monitored closely throughout their participation in the trial. In our Phase I sepsis-induced ARDS study, no subjects exceeded a COHb level of 10%, and there were no administration-associated AEs or study-related SAEs.

Risk of Blood Draws

All enrolled subjects will have blood drawn for both safety monitoring and research purposes. Most blood will be drawn through indwelling catheters. Risks of drawing blood percutaneously are uncommon and include bleeding and bruising.

Risk of Radiation Exposure

Most chest X-rays will be performed as part of usual ICU care. However, if not performed, we will obtain chest X-rays for endpoint assessment on the day after extubation (if the participant is extubated prior to day 7) and on day 7. The risk of ionization radiation from routine chest X-rays is generally considered minimal due to the low dose (~0.1 milliSievert [mSv]).

3.3.2 KNOWN POTENTIAL BENEFITS

Study subjects may or may not receive any direct benefits from their participation in this study. Our preclinical data demonstrate that low dose iCO is protective in experimental models of ALI. Numerous studies have shown CO to be cytoprotective in animal models of lung injury including hyperoxia and endotoxin exposure, bleomycin, ischemia/reperfusion, pneumococcal pneumonia, and VILI^{34,35,40,55-60,64}. Furthermore, CO has been shown to decrease inflammation, enhance phagocytosis, and improve mortality in models of sepsis including endotoxemia^{36,61,127}, hemorrhagic shock^{63,128-130}, and CLP^{42,43,53}. In addition, CO has been shown to have beneficial therapeutic effects in pre-clinical models of other diseases including traumatic brain injury (TBI)¹³¹, kidney fibrosis¹⁰⁵, colitis^{100,102}, arthritis¹⁰⁴, organ transplantation^{58,59,76-84}, hepatitis^{98,99}, and vasculopathies of the heart and lung^{67,72-74,94}.

Potential benefits from the administration of iCO include decreased requirement for ventilatory support, decreased days spent in the ICU, increased organ failure free days, and enhanced survival. Finally, there are potential benefits to society as the discovery of effective therapies that can reduce the substantial morbidity and mortality of ARDS or the identification of biomarkers that might improve prediction and monitoring of ARDS disease severity would enhance the health of society.

In addition to the potential benefit of iCO administration, all subjects, including those randomized to placebo, will benefit from protocolized low tidal volume ventilation and weaning protocols, as these have been shown to be beneficial in prior studies and are recommended in evidence-based consensus guidelines as best practice. As this protocol incorporates best practice guidelines, participation in the study will reduce the unexplained or potentially harmful variability in the application of such guidelines, and thus likely improve care, for all participants in our trial, including those participants randomized to placebo. Furthermore, there may be salutary effects on all participants given the additional clinical personnel and monitoring that will occur during administration of the study products.

3.3.3 ASSESSMENT OF POTENTIAL RISKS AND BENEFITS

Federal regulations at 45 CFR 46.111 (a)(2) require that “the risks to subjects are reasonable in relation to anticipated benefits, if any, to subjects, and the importance of the knowledge that may reasonably be expected to result.” There are several elements of study design in the present protocol that meets this human subject protection requirement. Several of the exclusion criteria prohibit participation of patients who might be at increased risk from the effects of iCO. These include individuals with severe hypoxemia, acute myocardial infarction (MI), stroke within 1 month, cardiac arrest requiring CPR within 72 hours, or inability to assess mental status following cardiac arrest, angina pectoris with activities of daily living, cardiopulmonary disease (NYHA class IV), as well as women who are pregnant or breastfeeding. In addition, to ensure the safety of subjects and minimize potential risks related to the study drug administration, our study protocol includes stringent monitoring of subjects, provisions for daily hold parameters, criteria for interruption of dosing, and permanent discontinuation of the study drug.

Based on the preceding assessment of risks and potential benefits, the risks to subjects are reasonable in relation to anticipated benefits, and commensurate with those inherent in the subjects' expected critical illness

requiring ICU care. There are currently no alternative available approaches to treat ARDS itself, besides supportive care, treatment of the underlying disease (eg. infection), and lung protective ventilator strategies. In addition, there are currently no biomarkers to assess disease severity and outcomes in ARDS. The potential risks of participation include those related to blood draws, chest X-rays, and those related to iCO treatment.

Blood draws: All enrolled subjects will have blood drawn for both safety monitoring and research purposes. Most blood will be drawn through indwelling catheters. Risks of drawing blood percutaneously are uncommon and include bleeding and bruising. The risks associated with this common clinical practice are small, whereas the knowledge gained in furthering our understanding of ARDS and development of a potential new therapy for patients with ARDS may be substantial.

Radiation Exposure: Most chest X-rays will be performed as part of usual ICU care. The risk of ionization radiation from routine chest X-rays is generally considered minimal due to the low dose (~0.1 milliSievert [mSv]).

CO Treatment: Data from animal studies demonstrate that low dose iCO has beneficial effects on outcomes in models of ALI. There is potential benefit to society and individual patients should iCO treatment prove to be beneficial for future patients with ARDS. Potential risks of high doses of the active study drug include headache and tachycardia. In cases of overdose, patients can have nausea, vomiting, seizures, problems thinking, coma, cardiopulmonary arrest, and death. These adverse effects are seen at doses much higher than those proposed in this study. Although there is a risk of toxicity associated with inhalation of high concentrations of CO, low dose iCO has been shown to be protective in animal models and safe in humans. No protocol-specified iCO administration-related AEs occurred in 8 subjects treated with low dose iCO in our prior Phase I trial.

Subjects will be vigilantly monitored for side effects during drug administration and COHb and lactate levels will be carefully monitored as outlined. There may be other risks of iCO in patients with ARDS that are currently unknown. Subjects will be monitored closely throughout their participation in the trial.

4 OBJECTIVES AND ENDPOINTS

4.1 PRIMARY OBJECTIVE

To evaluate the safety, tolerability, and efficacy of inhaled carbon monoxide (iCO), as well as to examine the biologic readouts of low dose iCO therapy in patients with ARDS.

4.2 HYPOTHESES

- Low dose iCO will be safe and well-tolerated and will reduce mtDNA levels in ARDS patients.
- Low dose iCO will reduce the severity of lung injury and non-pulmonary organ failure in ARDS patients.
- Low dose iCO will reduce mitochondrial dysfunction, attenuate inflammasome activation, and promote resolution of inflammation in ARDS patients. Furthermore, modulation of these pathways will predict improvements in the clinical outcomes.

4.3 PRIMARY SAFETY ENDPOINT

The primary safety endpoint is to evaluate the safety of inhaled CO, by determining COHb levels and the incidence of pre-specified administration-related adverse events.

- Safety of inhaled CO, defined by the incidence of pre-specified administration-related AEs (as defined below) and spontaneously reported AEs through study day 7.
 - Acute MI within 48 hours of study drug administration
 - Acute cerebrovascular accident (CVA) within 48 hours of study drug administration
 - New onset atrial or ventricular arrhythmia requiring DC cardioversion within 48 hours of study drug administration
 - Increased oxygenation requirements defined as: an increase in FiO_2 of ≥ 0.2 **AND** increase in $\text{PEEP} \geq 5$ cm H_2O within 6 hours of study drug administration
 - Increase in COHb $\geq 10\%$
 - Increase in lactate by ≥ 2 mmol/L within 6 hours of study drug administration

4.4 PRIMARY EFFICACY ENDPOINT

The primary efficacy endpoint is to compare the effects of iCO versus placebo on mtDNA levels from baseline to day 5 (or death, whichever comes first) in patients with ARDS.

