9.1.1 STUDY SAMPLE COLLECTION

Sample collection will be done according to the **Time-Events Schedule** in **Section 1.3**.

COHb Levels: COHb levels will be measured using the IL GEM Premier Co-oximeter at specified time points on Days 1 through 3. See **Section 9.5.2**.

Plasma Samples: Blood (4 mL on days 1-3) will be collected pre-treatment in EDTA anti-coagulated tubes for plasma isolation and measurement of biomarkers of mitochondrial dysfunction, inflammasome activation, lipid mediators, and cytokines. Blood will be collected (4 mL on days 1-3) post-treatment (at 90 min and 3 hrs). Blood (4 mL) will also be collected for plasma isolation on Day 5. Plasma will be obtained and divided immediately after centrifugation into equal aliquots in specified tubes and frozen at -80°C .

RNA Samples: On days 1-3, blood (2.5 mL) will be collected in Paxgene tubes for RNA isolation. Blood will be collected in Paxgene tubes before and after (at 90 min and 3 hrs) study drug administration, and frozen at -80°C . Blood (2.5 mL) will also be collected in Paxgene tubes for RNA isolation on Day 5, and frozen at -80°C .

DNA Samples: Cell pellets will be obtained for future DNA isolation from the blood collected in EDTA tubes on days 1-3 and on day 5. Cell pellets will be isolated pre-treatment and post-treatment (at 90 min and 3 hrs) on days 1 through 3. On days 1 and 5, the 8 mL tube may be used to isolate cell pellets if unable to obtain an adequate pellet from the 4 mL tube on that day.

Primary Cell Isolation: An additional 8 mL of blood will be drawn for isolation of peripheral blood mononuclear cells (PBMCs) pre-treatment on day 1 and post-treatment on day 3.

Urine Sample Collection: Between 50-100 mL of urine will be collected in a sterile specimen container on days 1-3 and on Day 5. Cell pellets will be isolated pre-treatment and post-treatment (at 90 min and 3 hours) to obtain RNA and protein, as well as mtDNA.

Discarded Specimens: Discarded bronchoalveolar lavage (BAL) fluid and plasma will be obtained (when available) for levels of cytokines, mediators/biomarkers, and protein. Plasma and BAL fluid will be divided into equal aliquots in specified tubes and frozen at -80°C .

A total of approximately 88.5 mL of blood will be collected for research samples during the study from each study subject as follows:

Sample collection	Day 1	Day 2	Day 3	Day 5	Total Volume
ABG, lactate, and COHb analysis	2.5 mL	2.5 mL	2.5 mL		7.5 mL

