10.2 SAMPLE SIZE DETERMINATION

A total of 32 subjects will be enrolled accounting for a 10% of loss of follow up. Sample size is based on 80% power to detect a difference in change from baseline to day 5 (or death whichever comes first) in mtDNA. With 16 subjects in the placebo arm and 16 subjects in the iCO arm, we will have 80% power to detect a 17225 absolute difference in change in mtDNA (copies/ μ l) from baseline to day 5 (or death whichever comes first) between treatment arms, assuming a conservative 14011 standard deviation (SD)¹⁶⁶ (Table 4). We will also have 80% power to detect a 0.98 difference in LIS, 81 mm Hg difference in PaO₂/FiO₂, and a 0.147 difference in Vd/Vt between treatment arms, assuming an SD of 0.8, 66, and 0.12 respectively^{167,168} (Table 5). With 16 patients randomized to iCO (Table 6), there will be a 77% probability of observing at last one AE that has a 10% background rate and a 96% probability of observing at least one AE that has a 20% background rate.

With 16 patients to each arm, we demonstrated differences in proportions with 2-sided 5% alpha (Table 7).

Table 4. Minimal Detectable Difference at 80% Power for Primary Outcome

Endpoint	Expected Mean Change in Placebo Arm	Expected Mean Change in iCO Arm	Standard Deviation	Detectable Absolute Difference (alpha=5%)
Change in mtDNA (copies/ μ l)	13348	-3877	14011	17225

Table 5. Minimal Detectable Difference on Day 7 at 80% Power for Secondary Endpoints

Endpoint	Detectable Absolute Difference on Day 7 (alpha=5%)	Standard Deviation
LIS	0.98	0.8
PaO ₂ /FiO ₂	81	66
OI	12.4	10.097
Vd/Vt	0.147	0.120
Vasopressor free days	5.2	4.2
Ventilator free days	13.7	11.2
ICU free days	12.6	10.3

Table 6. Probability of observing 1 or more events on the iCO arm for different background AE rates.

n	Background AE rate	Probability to detect ≥ 1 AE
16	0.010	0.13
16	0.020	0.25
16	0.035	0.39
16	0.050	0.51
16	0.100	0.77
16	0.150	0.90
16	0.200	0.96

Table 7. Adverse Events: Differences in proportions that can be demonstrated with 16 on each arm, 2-sided 5% alpha.

Placebo Proportion	iCO Proportion	Difference	Power
0.40	0.0191	0.3809	0.80
0.40	0.0042	0.3958	0.85
0.40	0.0000	0.4000	0.90
0.45	0.0459	0.4041	0.80
0.45	0.0293	0.4207	0.85
0.45	0.0103	0.4397	0.90
0.50	0.0762	0.4238	0.80
0.50	0.0580	0.4420	0.85
0.50	0.0370	0.4630	0.90

PASS version16, test for two proportions, unpooled
variance

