10.4.2 ANALYSIS OF THE PRIMARY EFFICACY ENDPOINT

We will use the Mann-Whitney U test to compare changes in mtDNA (copies/ μ l) from baseline to day 5 (or death whichever comes first) between treatment arms. Log transformed mtDNA will be analyzed using repeated measures analysis of covariance (ANCOVA) to assess the effects of treatment, time, and the interaction between time and treatment, while incorporating between-patient variation in baseline measurements and important covariates including age and severity of ARDS (SAS PROC MIXED). Interaction contrasts will include polynomial trends across time, focusing on a linear trend suggesting improvement and a quadratic trend suggesting that improvement is leveling off. As part of our analysis, we will also include the interaction between treatment and ARDS severity in the model. Because the study is not powered for the interaction between treatment and severity of ARDS, this test will be exploratory. We will also perform post-hoc analyses within each severity group to generate hypotheses for future study.

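### The primary mtDNA endpoint lets death replace Day 5 with no sample tied to death, so an early death would be scored on a shorter, possibly favourable window

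*Combined protocol and SAP*

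**What the plan says.** - **Endpoint.** Section 4.4 compares the arms on "mtDNA levels from baseline to day 5 (or death, whichever comes first) in patients with ARDS". The same substitution of death for Day 5 appears in the synopsis and in sections 2, 10.1, 10.2 and 10.4.2.
- **Primary test.** Section 10.4.2 states "We will use the Mann-Whitney U test to compare changes in mtDNA". It then adds a repeated-measures ANCOVA of log mtDNA and does not say which of the two analyses governs.
- **Sampling.** Section 9.1.1 schedules plasma on Days 1-3 before treatment and at 90 minutes and 3 hours, and says that blood "will also be collected for plasma isolation on Day 5". The schedule in section 1.3 agrees. No sample is triggered by death. Discarded clinical plasma is collected only where a site has it.
- **Planning values.** In Table 4 (section 10.2), the column "Expected Mean Change in Placebo Arm" holds +13,348 copies/µl. The iCO entry is -3,877, and the SD is 14,011.
- **Deaths.** No section supplied gives a missing-data rule or says which value represents a patient who dies before Day 5. Section 10.4.1 (General Approach) refers further detail to a Statistical Analysis Plan whose rules on this point are not in the supplied text.
- **Biology.** Section 3.1 says that circulating mtDNA is associated with mortality in critical illness.

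**The concern.** A Mann-Whitney test needs one change value per patient. For a death before Day 5, the only value available is from an earlier scheduled sample. Survivors are scored over Day 1 to Day 5; a patient who dies may be scored over hours or a day or two.

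On a scale where untreated patients are expected to rise, a shorter window tends to record a smaller change, and a smaller change counts as better. Since the protocol itself links mtDNA with mortality, this truncation is unlikely to be unrelated to the outcome.

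At stake is the meaning of the primary efficacy result. An imbalance in early deaths could move the rank test for reasons other than an effect on mtDNA: an excess on iCO could push it towards apparent benefit, and deaths confined to placebo could hide part of a real effect. With 16 patients per arm, a few deaths are enough to matter.

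**Working it through.** **Inputs.** Mean changes, SD and 16 per arm come from section 10.2. I take baseline as the Day 1 pre-dose sample, because the schedule shows no plasma isolation in the baseline column. Added assumptions: normal changes, a two-sided 5% test (one-sided 2.5% for false benefit), and the number and mtDNA course of early deaths, none of which the documents give.

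**Step 1. The plan's own figures.** 13,348 - (-3,877) = 17,225 reproduces the stated difference (17,225/14,011 = 1.23 SD). The stated 80% power does not reproduce at alpha 5%: a t-test gives 92% with 16 per arm and 88% with 14. The plan is conservative there, and nothing below depends on it.

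**Step 2. Where a carried value would rank.** Share of expected placebo patients with a worse change than c = Φ((13,348 - c)/14,011).

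| Recorded change before death | c | Beats this share of placebo |
|---|---|---|
| None | 0 | Φ(0.953) = 83% |
| Linear rise, last sample Day 2 (1/4 of rise) | 3,337 | Φ(0.715) = 76% |
| Linear rise, last sample Day 3 (1/2 of rise) | 6,674 | Φ(0.476) = 68% |
| Steep rise | 20,000 | Φ(-0.475) = 32% |

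At c = 0, an SD of 12,000 to 20,000 moves the 83% to between 87% and 75%.

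In the iCO arm under Table 4, the share with a better change than zero is Φ(3,877/14,011) = Φ(0.277) = 61%. A zero-change death therefore ranks worse than about 61% of expected iCO patients.

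**Step 3. Effect on an arm mean.** A zero-change death improves the mean by 13,348/16 = 834 in an arm expected to rise by 13,348. Under Table 4 it worsens the iCO mean by 3,877/16 = 242.

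**Step 4. False benefit when iCO has no mtDNA effect.** Simulation with both arms N(13,348, 14,011), 16 per arm, one-sided 2.5% Mann-Whitney, and early deaths on iCO only:

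| Value carried by deaths | 2 deaths | 3 deaths | 4 deaths |
|---|---|---|---|
| Flat, N(0, 3,000) | about 5% | about 6-7% | about 10% |
| Half the rise, N(6,674, 10,000) | 3.4% | 4.0% | 5.0% |
| Averaging +20,000 | about 1-1.5% | about 1-1.5% | about 1% |
| Ranked worst | 0.2% or less | 0.2% or less | 0.2% or less |

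**Step 5. Power if Table 4 is true** (two-sided 5% Mann-Whitney, 16 per arm; 90% with no deaths):

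| Early deaths | Scored as zero change | Ranked worst |
|---|---|---|
| 4 iCO, 0 placebo | 91% | 5% |
| 0 iCO, 4 placebo | 74% | 99% |
| 2 per arm | 83-85% | about 70% |

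Under zero-change scoring, four iCO-only deaths leave the primary test unmoved, and four placebo-only deaths reduce its power.

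**The case against.** **Carry-forward is not written down.** True. The supplied text names no last-sample rule, and detail is deferred to a separate plan. But the endpoint does name death as an alternative endpoint time, and the scheduled samples leave no other value to use. If carry-forward is not intended, the primary variable is undefined for these patients and still needs a rule.

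**The 83% is not a figure of the plan.** This stands. It needs a change of exactly zero and normality. The mtDNA-mortality link may mean that dying patients rise before their last sample, which would shrink or reverse the bias, as the last row of Step 2 and the third row of Step 4 show.

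**A reader might infer that deaths are scored as treatment successes, or that harm from iCO would appear as benefit.** The documents do not support that. Under Table 4, a zero-change iCO death ranks below most iCO patients, and power stays at about 90%. Inflation towards benefit appears only if iCO has no mtDNA effect, deaths fall mainly on iCO, and their mtDNA is flat or rises less than in survivors. Exclusion criterion 8 also removes patients not expected to survive 24 hours.

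**Other analyses cover it.** The repeated-measures model needs no carried value, section 10.4.3 analyses mortality by Cox regression, and section 9.7.6 sends in-hospital deaths to the DSMB. Excess deaths would therefore be seen. None of this repairs the Mann-Whitney comparison, which is named first for the primary endpoint.

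**Worst ranks change the question.** This also stands. They turn a biomarker comparison into a composite of death and mtDNA and cost power when deaths are balanced.

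**Conclusion.** The concern holds in a limited form. The endpoint wording, the sampling schedule and a test needing one change per patient together mean that a death before Day 5 can enter the primary test only through an earlier sample over a shorter window, unless an unstated rule applies. Because placebo is expected to rise, that value can look favourable.

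Its rank against placebo runs from about 83% with no recorded change, through 76% or 68% under a linear rise, to 32% after a 20,000 rise. With no true mtDNA effect and two to four early deaths on iCO alone, one-sided false benefit runs from about 5-10% (flat) through about 3-5% (half the rise) to below the nominal 2.5% (steep rise). These figures rest on assumed death counts, trajectories and normality. The direction and size of bias in the actual trial are unknown.

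**What to change.** In sections 4.4, 10.2 and 10.4.2, and wherever the endpoint is repeated, stop treating a pre-death sample as equivalent to Day 5. State before unblinding how deaths before the Day 5 sample enter the rank test.

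At minimum:

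- pre-specify a sensitivity analysis in which these deaths take the worst ranks, ordered by time of death;
- report it beside the survivors-only Day 5 comparison and the number of deaths before Day 5 by arm;
- claim benefit only if the worst-rank result does not contradict it.

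The cost is wording and one further analysis, with no new patients or samples. The worst-rank analysis answers a composite death-mtDNA question, and with two deaths per arm its power is about 70%, against about 83-85% under zero-change scoring. Whether to make it primary is therefore the sponsor's choice. If it is made primary, the mtDNA copy-number difference should be reported separately.

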4.5 SECONDARY ENDPOINTS

The secondary endpoints will examine the effects of iCO versus placebo on the following outcomes:

- Lung Injury Score (LIS) on days 1-5, and 7
- $\text{PaO}_2/\text{FiO}_2$ ratio on days 1-5, and 7
- Oxygenation Index (OI) on days 1-5, and 7
- Dead Space Fraction (Vd/Vt) on days 1-3, and 7
- Sequential Organ Failure Assessment (SOFA) score on days 1-5, 7, 14, 28

Additional secondary endpoints will examine the effects of iCO versus placebo on biomarkers of mitochondrial dysfunction, inflammasome activation, and lipid mediators in patients with ARDS.

- Autophagy markers (eg. LC3B)
- Inflammasome-dependent cytokines (eg. IL-18)
- Lipid mediators (LM) and specialized pro-resolving mediators (SPMs)
- Mitochondrial quality control biomarkers (eg. Pink1, Wipi1)
- Biomarkers of inflammation (eg. IL-6, IL-8, IL-10, IL-1Ra)
- To enhance the biologic analytic power, samples from 12 subjects enrolled in a similar, already completed study will be similarly analyzed for these biomarkers, as well as in more extensive biologic 'omics profiling that will permit more detailed analyses of these pathways in correlation with clinical data.

